Study Design	
This is a single-center Phase 1b open-label, study of PSMA-targeted radionuclide therapy with ^{177}Lu-PSMA-617 in combination with pembrolizumab in patients with mCRPC who have previously progressed on at least one prior androgen pathway inhibitor (e.g. abiraterone, enzalutamide, apalutamide). Patients must have at least three metastatic lesions which are PSMA-avid on baseline ^{68}Ga-PSMA-11 PET imaging.
 
In Part A of the study, patients will be enrolled sequentially into one of three treatment schedules with respect to timing of ^{177}Lu-PSMA-617 in relation to first dose of pembrolizumab (N = 6 patients per schedule):
 
Schedule 1) Priming dose of ^{177}Lu-PSMA-617 administered on Cycle 1 Day 1 followed by pembrolizumab 200 mg IV q 21 days starting Cycle 2 Day 1.
 
Schedule 2) Priming dose of ^{177}Lu-PSMA-617 administered concurrently with initiation of pembrolizumab on Cycle 1 Day 1.
 
Schedule 3) Priming dose of ^{177}Lu-PSMA-617 administered on Cycle 1 Day 1 following initiation of pembrolizumab on Cycle 1 Day -21.
 
The dose-limiting toxicity window will be Cycle 1 + Cycle 2 (i.e. 6 weeks following C1D1 administration of Lu-PSMA-617 across) in all three Schedule cohorts.
 
In Part A of the study, 6 patients will be enrolled to Schedule 1, then 6 patients to Schedule 2, and finally 6 patients will be enrolled to Schedule 3.
 
The starting dose of ^{177}Lu-PSMA-617 will be 7.4 +/- 15% GBq, which is the recommended phase 3 dose of the agent. If the DLT frequency attributable to Lu-PSMA exceeds 33% at any point after 6 evaluable patients have been enrolled in Part A, Dose Level -1 of ^{177}Lu-PSMA-617 will be investigated (4 Gbq +/- 15%) for the remainder of patients enrolled on study.
 
Using the data obtained in Part A, the recommended phase 2 dose and schedule of ^{177}Lu-PSMA-617 will be determined by the Principal Investigator using a combination of safety, efficacy, and immunologic effects of treatment from the first two cycles (and additional cycles of treatment when available).
 
In Part B of the study, an additional 25 patients will be enrolled at the recommended phase 2 dose and schedule to obtain additional safety, efficacy, and immunologic data pertaining to the treatment combination.

--------------	--

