3.1 Characteristics

This is a single-center Phase 1b open-label, study of PSMA-targeted radionuclide therapy with ¹⁷⁷Lu-PSMA-617 in combination with pembrolizumab in patients with mCRPC who have previously progressed on at least one prior androgen pathway inhibitor (e.g. abiraterone, enzalutamide, apalutamide). Patients must have at least three metastatic lesions which are PSMA-avid on baseline ⁶⁸Ga-PSMA-11 PET imaging.

In **Part A** of the study, patients will be enrolled in sequential fashion to one of treatment schedules with respect to timing of ¹⁷⁷Lu-PSMA-617 in relation to first dose of pembrolizumab (N = 6 evaluable patients per schedule):

Schedule 1) Priming dose of ¹⁷⁷Lu-PSMA-617 administered on Cycle 1 Day 1 followed by pembrolizumab 200 mg IV q 21 days starting Cycle 2 Day 1.

Schedule 2) Priming dose of ¹⁷⁷Lu-PSMA-617 administered concurrently with initiation of pembrolizumab on Cycle 1 Day 1.

Schedule 3) Priming dose of ¹⁷⁷Lu-PSMA-617 administered on Cycle 1 Day 1 following initiation of pembrolizumab on Cycle 1 Day -21.

The priming dose of ¹⁷⁷Lu-PSMA-617 will be 7.4 +/- 15% GBq, which is the recommended phase 3 dose of the agent. If the DLT frequency exceeds 33% including patients across the three schedules, Dose Level -1 of ¹⁷⁷Lu-PSMA-617 will be investigated (4 Gbq +/- 15%).

6 evaluable patients will be enrolled in each of the three cohorts in sequential fashion in Part A of the study. The DLT window will be Cycle 1 + Cycle 2. If the DLT frequency is \geq 33% for a

particular cohort, that dosing schedule will be determined to be non-tolerable and the next schedule will be evaluated. In addition, if the DLT frequency attributable specifically to Lu-PSMA-617 is $\geq 33\%$ after 6 or more evaluable patients are enrolled in Part A of the study, the dose of Lu-PSMA-617 will be reduced to Dose Level -1 (4 GBq +/- 15%) for the remainder of patients enrolled on study. If the DLT frequency attributable to Lu-PSMA-617 at Dose Level -1 is $\geq 33\%$ after 6 or more patients are treated at Dose Level -1, study accrual will be halted.

Using the data obtained in Part A, the recommended phase 2 dose and schedule of ^{177}Lu -PSMA-617 will be determined by the DSMC and Principal Investigator using a combination of safety, efficacy, and immunologic effects of treatment from the first two cycles (and additional cycles of treatment when available).

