4.1.6 Dose Limiting Toxicities and Criteria for Dose De-Escalation

The starting dose level of ^{177}Lu -PSMA-617 is 7.4 GBq (+/- 15%).

Patients will be assessed for dose-limiting toxicities during Cycle 1 and 2 for patients enrolled in Part A of the study, defined as any of the following AEs occurring during Cycle 1 or 2:

- Any non-hematologic treatment-related AE \geq Grade 3, with the exceptions of Grade 3 nausea, vomiting, diarrhea, constipation, fever, fatigue, skin rash, or non-clinically significant laboratory abnormality that resolves to Grade \leq 2 within 72 hours with optimal medical management.
- Grade 4 thrombocytopenia, or Grade 3 thrombocytopenia with Grade > 1 bleeding or requirement for platelet transfusion.
- Grade 4 neutropenia lasting for > 5 consecutive days
- Grade ≥ 3 febrile neutropenia.

6 evaluable patients will be enrolled in each of the three cohorts in sequential fashion in Part A of the study. If the DLT frequency is $\geq 33\%$ for a particular cohort, that dosing schedule will be determined to be non-tolerable and the next schedule will be evaluated. In addition, if the DLT frequency attributable specifically to ^{177}Lu -PSMA-617 is $\geq 33\%$ after 6 or more evaluable patients are enrolled in Part A of the study, accrual will be temporarily halted and the dose of ^{177}Lu -PSMA-617 will be reduced to Dose Level -1 (4 GBq +/- 15%) for the remainder of patients enrolled on study. If the DLT frequency attributable to ^{177}Lu -PSMA-617 at Dose Level -1 is $\geq 33\%$ after 6 or more patients are treated at Dose Level -1, study accrual will be halted.

Patients who discontinue study for reasons other than treatment related toxicity during prior to the completion of two cycles of therapy, or those who discontinue study prior to receiving priming dose of ^{177}Lu -PSMA-617, will be considered inevaluable for purposes of DLT determination.

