⁷ Tumor biopsy will be performed during Screening and within 14 days preceding C3D1 visit. Screening biopsy must be performed prior to initiation of study treatment but is not subject to 28-day screening window. Bone biopsies are acceptable if no soft tissue lesion is amenable for biopsy. The same lesion should be selected for the follow up biopsy whenever feasible. PSMA-avid lesion should be prioritized for biopsy; non-PSMA avid lesion may be used if no PSMA-avid lesion is accessible.

⁸ Whole blood (40 mL in Na-Heparin green top tube) will be collected on C1D-21 (pre-dose), C1D1 (pre-dose), C2D1 (pre-dose), C3D1 (pre-dose), on Day 1 of every 3 cycles thereafter (e.g. C6D1, C9D1, etc), and at the time of disease progression.

⁹ SPECT/CT dosimetry scan is optional.

6 Reporting and Documentation of Results

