8.3 Interim Analyses

Patients in Part A will be evaluated for dose-limiting toxicities during the first two cycles of treatment as outlined above in Section 7.1.

In Part B, an interim safety analysis will be performed after 6 patients are enrolled. If the DLT frequency exceeds 33%, study accrual will be halted and alternative dose and schedule of Lu-PSMA-617 may be evaluated based on the prior results of Part A of the study.

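### The Schedule 3 pembrolizumab lead-in is not carried into two analysis rules: the PSA-response baseline falls on treatment, and a toxicity stop before Lu-PSMA never enters the cohort's 33% DLT rule.

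*Combined protocol and SAP*

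**What the plan says.** **Dosing.** In Schedule 3 Lu-PSMA is given on C1D1 "following initiation of pembrolizumab on Cycle 1 Day -21" (Section 3.1). In Schedules 1 and 2 no study drug precedes C1D1.

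**PSA.** Section 8.4.2 measures PSA response from the value drawn on C1D1. Section 7.7 asks for a reference value taken no more than two weeks before therapy starts. The Schedule 3 calendar (Section 5.4) collects PSA at screening, Day -21 and C1D1.

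**DLT evaluability.** Section 4.1.6 has two inevaluability clauses. The first covers patients who stop before completing two cycles for reasons other than treatment-related toxicity, so toxicity stops remain evaluable. The second adds "or those who discontinue study prior to receiving priming dose of" Lu-PSMA. Both groups "will be considered inevaluable for purposes of DLT determination". The second clause has no toxicity exception.

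**Cohort rule.** Sections 3.1 and 4.1.6 call a schedule non-tolerable at a DLT frequency of 33% or more among six evaluable patients, which is 2 of 6.

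**DLT window.** The synopsis (Study Design) explains it as "6 weeks following C1D1 administration of Lu-PSMA-617" in all three cohorts. Section 3.1 says "The DLT window will be Cycle 1 + Cycle 2". Section 8.3 says patients are "evaluated for dose-limiting toxicities during the first two cycles of treatment". The Day -21 visit carries a Cycle 1 label, for example in footnote 8 of Section 5.4, where blood "will be collected on C1D-21 (pre-dose), C1D1 (pre-dose").

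**The concern.** A baseline should precede all study treatment. In Schedule 3 the C1D1 PSA follows three weeks of pembrolizumab, so any early PSA movement shifts the meaning of a 50% decline in that schedule alone. Sections 7.7 and 8.4.2 cannot both be followed there.

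The second inevaluability clause is harmless in Schedules 1 and 2. In Schedule 3 it removes a patient whom pembrolizumab toxicity stops before C1D1. The protocol provides for such stops: Section 4.8 (pembrolizumab-related Grade 4 events) and Section 6.3.2.5 (toxicity that does not resolve). With a boundary of two patients, one uncounted event can change the tolerability call. Whether a DLT is actually lost depends on a window that the passages do not describe consistently.

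**Working it through.** **PSA**

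Let r be the C1D1 PSA divided by the pre-treatment PSA. A 50% fall from C1D1 is a fall of 1 - 0.5r from pre-treatment. The documents give no value of r; I assume 0.8 to 1.2.

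- r = 0.8: 1 - 0.40 = 60%
- r = 1.0: 50%
- r = 1.2: 1 - 0.60 = 40%

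**DLT rule**

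The plan gives no operating characteristics for this rule, so there is no stated figure to reproduce. The 93% power for the Part B response rate is not affected.

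Inputs from the documents: six evaluable patients and a limit of one third. Assumed, because the documents give no rates: q, the share of Schedule 3 starters with a DLT-grade stop in the lead-in (2%, 5%, 10%); and p, the DLT rate after C1D1 (10% to 30%).

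*As written.* Lead-in stops are excluded, so the chance of reaching the limit depends on p alone:

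P(X ≥ 2 of 6) = 1 - (1-p)^6 - 6p(1-p)^5

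At p = 15%: 1 - 0.3771 - 0.3993 = 22.4%.

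*Lead-in inside the window, stopped patients not replaced.* Each of six starters has a DLT with probability q + (1-q)p. At q = 5%, p = 15%: 0.05 + 0.95 × 0.15 = 0.1925, and P(X ≥ 2 of 6) = 32.6%.

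*Lead-in inside the window, stopped patients replaced.* Enrolment continues until six receive Lu-PSMA. L, the number of lead-in stops, is negative binomial, and X is binomial(6, p). The limit is reached if (L + X)/(6 + L) ≥ 1/3:

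- L = 0 or 1: X ≥ 2 is needed (2/7 = 28.6% is below the limit)
- L = 2: X ≥ 1 is needed
- L ≥ 3: always reached

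At q = 5%, P(L = 0, 1, 2, ≥3) = 0.7351, 0.2205, 0.0386, 0.0058. At p = 15%, P(X ≥ 2) = 0.2235 and P(X ≥ 1) = 0.6229. The total is 0.9556 × 0.2235 + 0.0386 × 0.6229 + 0.0058 = 24.3%.

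Chance of reaching the limit (%), with the excess over the rule as written in brackets:

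| q | p | As written | Counted, not replaced | Counted, replaced |
|---|---|---|---|---|
| 2% | 10% | 11.4 | 15.1 (3.7) | 11.7 (0.3) |
| 2% | 15% | 22.4 | 26.4 (4.1) | 22.7 (0.3) |
| 2% | 20% | 34.5 | 38.4 (3.9) | 34.8 (0.3) |
| 2% | 30% | 58.0 | 61.0 (3.0) | 58.2 (0.2) |
| 5% | 10% | 11.4 | 21.2 (9.8) | 13.3 (1.9) |
| 5% | 15% | 22.4 | 32.6 (10.3) | 24.3 (2.0) |
| 5% | 20% | 34.5 | 44.2 (9.8) | 36.4 (1.9) |
| 5% | 30% | 58.0 | 65.2 (7.2) | 59.4 (1.4) |
| 10% | 10% | 11.4 | 32.0 (20.6) | 18.8 (7.3) |
| 10% | 15% | 22.4 | 43.0 (20.7) | 29.8 (7.4) |
| 10% | 20% | 34.5 | 53.6 (19.1) | 41.4 (6.9) |
| 10% | 30% | 58.0 | 71.7 (13.7) | 63.0 (5.0) |

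At q = 0 nothing changes.

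*Lead-in outside the window.* No DLT is lost. Adding the stopped patients as non-DLTs would weaken the rule: the per-patient rate becomes (1-q)p, and at p = 15% the 22.4% falls to 21.6%, 20.6% and 18.9% for q = 2%, 5% and 10%.

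*How often it would arise.* The chance that at least one of six starters is stopped in the lead-in is 1 - (1-q)^6: 11.4%, 26.5% and 46.9%.

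**The case against.** The strongest reply is that the synopsis does define the window, as six weeks from C1D1 in all three cohorts. Two 21-day cycles make six weeks only on that count; including Day -21 gives nine. A patient never given Lu-PSMA then never enters the window, and the second clause is coherent. This stands: a reader might infer that the plan discards Schedule 3 DLTs, and on the synopsis text it does not. What remains is that the Cycle 1 label on Day -21, with the other descriptions of the window, leaves room for the opposite reading. On either reading the cohort rule is silent about patients stopped by that schedule's first drug.

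A reader might also infer that lead-in toxicity is hidden, or that schedule selection is biased towards Schedule 3. The documents do not support that. Adverse events are assessed from Day -21 (Section 5.4), patients are evaluable for toxicity from first study drug (Section 6.1.1), and all Grade 3-5 events are reviewed monthly (Appendix 2). The schedule is chosen on combined safety, efficacy and immunologic data (Section 3.1). The rule on DLTs attributable to Lu-PSMA is unaffected.

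The assumed rates are not estimates. Section 1.7.1 reports one DLT, in Schedule 2, among 14 patients (7.1%; exact 95% interval 0.2% to 34%) over all follow-up to that date. That neither points to a 10% lead-in stop rate nor excludes one.

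On PSA, Section 7.7 already has a pre-therapy reference, so this is a conflict between two sections on a descriptive secondary endpoint, not a uniformly on-treatment baseline. That is fair, but the analytic plan is where the C1D1 value is specified.

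Three further inferences are only conditional:

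- Section 6.2 limits safety analyses to patients given the radiotracer. It excludes lead-in stops only if that term means Lu-PSMA and not the screening PET agent.
- Section 3.5 replaces patients who withdraw. Section 5.1 lists withdrawal apart from toxicity, so it may not cover toxicity stops, although the target of six evaluable patients has the same effect.
- The Part B consequences arise only if Schedule 3 is selected.

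**Conclusion.** The point holds, at modest size.

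The PSA part is firm on the text. In Schedule 3 the C1D1 baseline is on treatment and cannot meet Section 7.7. Its numerical effect (60% to 40% in place of 50%) rests on an assumed lead-in change of -20% to +20%.

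The DLT part is a gap plus an ambiguity. If the window starts at C1D1, as the synopsis says, no DLT is lost and only separate reporting is missing. If the lead-in is inside, the chance of reaching the limit is understated as follows, for assumed later DLT rates of 10-30%:

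| Assumed lead-in stop rate | Not replaced | Replaced |
|---|---|---|
| 2% | 3-4 points | 0.2-0.3 points |
| 5% | 7-10 points | 1.4-2.0 points |
| 10% | 14-21 points | 5.0-7.4 points |

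The larger column should not be quoted alone: it needs both the wider window and no replacement. No net bias between schedules is shown.

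**What to change.** 1. **PSA baseline.** In Sections 7.7 and 8.4.2, use the last PSA before the first dose of any study drug in all schedules. For Schedule 3 the Day -21 sample already exists in the calendar; state that it must be drawn before the infusion.
2. **DLT window.** Reconcile the synopsis and Sections 3.1, 4.1.6, 5.4 and 8.3 on whether Day -21 to C1D1 is inside the window, and align Section 3.5 in the same amendment. This review does not propose which window is right.
   - If inside: count DLT-grade stops before Lu-PSMA in numerator and denominator, and state whether such patients are replaced. One such stop plus one later DLT is 2/6 = 33.3% without replacement and 2/7 = 28.6% with it.
   - If outside: do not add these patients as non-DLTs. Report lead-in toxicity stops by schedule beside the DLT rate when tolerability is judged.
3. **Secondary.** Define the term radiotracer in Section 6.2 so that it agrees with Section 6.1.1.
4. **Only if Schedule 3 goes to Part B.** Section 8.3 says "an interim safety analysis will be performed after 6 patients are enrolled"; state how lead-in stops are handled there. Also report the response rate in all patients who started study drug. If stopped patients are non-responders, 40% in Lu-treated patients becomes 0.40 × 0.98 = 39% to 0.40 × 0.90 = 36% at lead-in stop rates of 2% to 10%.

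**Cost.** No new visits or samples. It is a mid-study amendment, with 14 of about 18 Part A patients enrolled at the date in Section 1.7.1, so Schedule 3 results should be shown under the old and new rules. Schedule 3 may look less favourable. If the lead-in is inside the window, Schedule 3 is observed for 3 + 6 = 9 weeks against 6 in the others, which should be stated when schedules are compared.

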4.1.7 Contraindications to ^{177}Lu -PSMA-617

Hypersensitivity to the active substance or to any of the excipients.

4.1.8 Adverse reactions to ^{177}Lu -PSMA-617

- Nausea
- Fatigue
- Xerostomia
- Hypogeusia
- Anorexia
- Bone pain

- Dry eyes
- Thrombocytopenia
- Neutropenia
- Anemia

4.1.9 Drug interactions

There are no known drug interactions with ^{177}Lu -PSMA-617.

4.1.10 Warnings and precautions

General warnings and precautions

Given the tolerance profile of ^{177}Lu -PSMA, it is not recommended to start a treatment in the following cases:

- Previous external beam radiotherapy involving more than 25% of the bone marrow
- Renal failure with serum creatinine $> 1.5 \text{ mg/dL}$ or estimated creatinine clearance $< 50 \text{ mL/min}$
- Impaired hematological function with either $\text{Hb} < 9 \text{ g/dL}$, platelets $< 100 \times 10^9/\text{L}$, or $\text{ANC} < 1.5 \times 10^9/\text{L}$

Radiation exposure

See **Appendix 4 and 5** for full details regarding protection from radiation exposure.

It is recommended that the patient urinate as much as possible during this period. Urine and feces should be disposed according to the regulation. The patient can leave the controlled area or the hospital only when radiation exposure to third parties does not exceed regulatory thresholds.

As long as there is no accidental contamination, such as from the leakage of the infusion system or because of urinary incontinence, radioactivity contamination is not expected on the patient's skin. However, it is recommended that when conducting standard care or exams with medical devices or other instruments which contact the skin (e.g. ECG), basic protection measures be observed such as wearing gloves, installing the material/electrode before the start of radiopharmaceutical infusion, changing the material/electrode after measurement, and eventually monitoring the radioactivity of equipment after use.

At the time of release, patients are given written instructions (**Appendix 5**) which outline the precautions the patient must take to minimize radiation exposure to people around them.

Men of childbearing potential

Ionizing radiations of ^{177}Lu -PSMA-617 may potentially have temporary toxic effects on male gonads. Due to the presence of the radionuclide in the product, men of childbearing potential must refrain from childbearing by using effective contraception methods during treatment with ^{177}Lu -PSMA and for 2 months after last dose.

Fertility

Fertility can be temporarily affected in men due to radiation damage to Sertoli cells, as evidenced by a decrease of inhibin-B and a concomitant increase of FSH (Teunissen et al., 2009). Fertility is usually restored 12 to 18 months after treatment. Cryopreservation of sperm might be offered to male patients before treatment.

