3.3 Eligibility Criteria

Patients must have baseline evaluations performed prior to Cycle 1 Day 1 of treatment and must meet all inclusion and none of the exclusion criteria. In addition, the patient must be thoroughly informed about all aspects of the study, including the study visit schedule and required evaluations and all regulatory requirements for informed consent. The written informed consent must be obtained from the patient prior to enrollment. The following criteria apply to all patients enrolled onto the study unless otherwise specified.

Inclusion Criteria

Part A:

- (1) The subject is able and willing to comply with study procedures and provide signed and dated informed consent.
- (2) Male participants who are at least 18 years of age on the day of signing informed consent.

(3) Histologically confirmed prostate adenocarcinoma. *De novo* small cell neuroendocrine prostate cancer will not be allowed due to putative lower PSMA expression in this tumor subtype. Treatment-emergent small cell neuroendocrine prostate cancer detected in metastatic tumor biopsy is not an exclusion.

(4) A minimum of three PSMA-avid lesions on baseline ^{68}Ga -PSMA-11 PET, with positive lesions defined as those with SUV_{max} values greater than liver.

(5) Progressive metastatic castration-resistant prostate cancer by PCWG3 criteria at the time of study entry.

(6) Castrate level of serum testosterone at study entry (< 50 ng/dL). Patients without prior bilateral orchiectomy are required to remain on LHRH analogue treatment for duration of study

(7) Prior progression on at least one second generation androgen signaling inhibitor including abiraterone, apalutamide, darolutamide, and/or enzalutamide.

(8) Adequate hematologic, renal, and liver function, defined as:

- Absolute neutrophil count $> 1.5 \times 10^9/\text{L}$
- Hemoglobin $> 9.0 \text{ g/dL}$
- Platelet count $> 100,000/\text{microliter}$
- Serum creatinine $\leq 1.5 \times \text{ULN}$ or estimated GFR $> 50 \text{ ml/min}$ by Cockcroft-Gault or 24 hour urine collection.
- Total bilirubin $\leq 1.5 \times \text{ULN}$. In patients with known or suspected Gilbert's disease, direct bilirubin $\leq \text{ULN}$.
- Aspartate aminotransferase and alanine aminotransferase $\leq 2.5 \times \text{ULN}$ ($\leq 5 \times \text{ULN}$ in patients with liver metastases).

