(16) Has clinically significant cardiovascular disease including, but not limited to:

- Uncontrolled or any New York Heart Association Class 3 or 4 congestive heart failure.
- Uncontrolled angina, history of myocardial infarction, unstable angina or stroke within 6 months before study entry.
- Clinically significant arrhythmias not controlled by medication. Chronic rate controlled or paroxysmal atrial fibrillation/flutter is not an exclusion to study participation.

- (17) Prior external beam radiation involving $\geq 25\%$ of bone marrow or within 14 days of start of protocol therapy.
- (18) Major surgery within 28 days of study treatment. Note: If participant received major surgery, they must have recovered adequately from the toxicity and/or complications from the intervention prior to starting study treatment.
- (19) Has an active infection requiring systemic therapy
- (20) Has a known history of HIV (screening not required).
- (21) Has a known history of Hepatitis B (defined as Hepatitis B surface antigen [HBsAg] reactive) or known active Hepatitis C virus (defined as HCV RNA [qualitative] is detected) infection (screening not required)
- (22) Has a known history of active TB (Bacillus Tuberculosis).
- (23) Has known psychiatric or substance abuse disorders that would interfere with cooperation with the requirements of the trial.
- (24) Any condition that, in the opinion of the Principal Investigator, would impair the patient's ability to comply with study procedures
- (25) History of bleeding diathesis and not currently on anti-coagulation therapy that cannot be safely discontinued for the tumor biopsy procedure.

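### The renal entry rule admits some men whom the protocol's own drug precaution advises against treating with 177Lu-PSMA

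*Combined protocol and SAP*

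**What the plan says.** Section 3.3 states that patients "must meet all inclusion and none of the exclusion criteria". The renal part of inclusion 8 sets a creatinine ceiling of 1.5 x ULN, then adds "or estimated GFR $> 50" mL/min, by Cockcroft-Gault or 24-hour urine collection. One of the two is enough.

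Section 4.1.10 says that "it is not recommended to start a treatment in the following cases", and its renal case is "Renal failure with serum creatinine $> 1.5" mg/dL "or estimated creatinine clearance $< 50" mL/min. One of the two is enough to trigger the advice.

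None of the 25 exclusion criteria concerns renal function. The only contraindication listed in Section 4.1.7 is "Hypersensitivity to the active substance or to any of the excipients". Nothing in the protocol says which renal rule takes precedence.

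**The concern.** An entry rule and a precaution on the same organ should be complements: whoever passes the first should not be caught by the second. Here both are joined by 'or', so a man can pass on one measure and be flagged on the other. The creatinine limits also differ in kind, a multiple of the laboratory's ULN at entry against a fixed 1.5 mg/dL in the precaution.

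The stakes are patient safety and consistent screening. Staff who apply Section 3.3 alone would enrol and dose a man whom the drug section advises against treating. An investigator who gives weight to 4.1.10 would turn the same man away. The protocol treats the kidney as relevant: Section 1.2 lists it among normal tissues that express PSMA, and Section 4.1.4 requires intravenous fluids for renal protection. No endpoint, sample size or analysis depends on this.

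**Working it through.** The plan states no figure to reproduce. The check is a comparison of two rules, followed by worked cases.

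**The rules side by side**

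- Eligible (inclusion 8): creatinine <= 1.5 x ULN **or** GFR > 50 mL/min.
- Advised against (4.1.10): creatinine > 1.5 mg/dL **or** clearance < 50 mL/min.
- The exact complement of the second rule is creatinine <= 1.5 mg/dL **and** clearance >= 50 mL/min. Inclusion 8 is looser in its logic and, wherever ULN is above 1.0 mg/dL, in its creatinine limit.

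**Inputs for the cases**

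- Clearance: Cockcroft-Gault, the formula named in inclusion 8, in its standard form for men: (140 - age) x weight / (72 x creatinine).
- ULN for creatinine: not in the documents; assumed to be 1.0 to 1.3 mg/dL.
- Ages, weights and creatinine values: illustrative assumptions.

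**Cases**

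| Man | Clearance (mL/min) | Inclusion 8 | 4.1.10 |
|---|---|---|---|
| 80 y, 65 kg, 1.2 mg/dL | 60 x 65 / 86.4 = 45.1 | Eligible on creatinine at every ULN in the range | Advised against: clearance < 50 |
| 78 y, 75 kg, 1.4 mg/dL | 62 x 75 / 100.8 = 46.1 | Eligible on creatinine at every ULN in the range | Advised against: clearance < 50 |
| 65 y, 90 kg, 1.7 mg/dL | 75 x 90 / 122.4 = 55.1 | Eligible on GFR whatever the ULN | Advised against: creatinine > 1.5 |
| 75 y, 80 kg, 1.8 mg/dL | 65 x 80 / 129.6 = 40.1 | Eligible at ULN 1.2 or 1.3, not at 1.0 or 1.1 | Advised against on both measures |

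**Where clearance falls below 50.** Setting the formula equal to 50 gives creatinine = (140 - age) x weight / 3600:

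- 80 y, 65 kg: 60 x 65 / 3600 = 1.08 mg/dL
- 78 y, 75 kg: 62 x 75 / 3600 = 1.29 mg/dL
- 75 y, 80 kg: 65 x 80 / 3600 = 1.44 mg/dL

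All three lie below 1.5 mg/dL, so older or lighter men enter the gap at creatinine values that inclusion 8 accepts at any ULN in the range.

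**The unit mismatch alone.** 1.5 x ULN is 1.50, 1.65, 1.80 and 1.95 mg/dL for ULN of 1.0, 1.1, 1.2 and 1.3. A creatinine above 1.5 mg/dL and up to that limit is always eligible and always advised against. At ULN 1.0 this particular gap disappears.

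**The other items in 4.1.10.** The blood-count item, which opens "Impaired hematological function with either", uses hemoglobin 9 g/dL, platelets 100 x 10^9/L and ANC 1.5 x 10^9/L, the same cut-offs as inclusion 8. The marrow-irradiation item uses 25%, as does exclusion 17 ("Prior external beam radiation involving"). At the exact boundary, eligibility is slightly stricter than the precaution, so neither item leaves a gap. Only the renal item is looser at entry.

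**The case against.** The strongest reply is that the two sections do different jobs. Section 3.3 decides who may enter; 4.1.10 advises on starting the drug. An investigator who reads both would not dose such a man without choosing to depart from the advice. That is fair, and it limits the consequence. It does not reconcile the rules, because the protocol turned the other two advisory items into firm entry criteria and gives no order of precedence here.

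The words 'renal failure with' might narrow the precaution, so that a man with creatinine 1.7 mg/dL and clearance 55 mL/min is not meant. The blood-count item has a similar form, though, and there the numbers define the condition; no other definition of renal failure is given. Even on the narrower reading, the cases with clearance below 50 mL/min remain.

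The either-or entry rule may be deliberate. The documents do not settle intent, which is why the remedy can run in either direction.

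Renal risk may also be low. One priming dose is planned, hydration is required, and chemistry including creatinine is scheduled at screening, on Cycle 1 Day 1 and on Days 8 and 15. In Part A the DLT definition covers treatment-related non-hematologic events of Grade 3 or above, with listed exceptions. The earlier phase 2 table in Section 1.7.1 shows 0% renal toxicity at both grade levels. All of this supports a low severity. It does not answer the point, since that study's renal entry limits are not given and its 0% may not cover these men.

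**Conclusion.** The inconsistency is real: the renal entry rule is wrong as written when set against the protocol's own precaution, and the point is minor. That some eligible men fall under the precaution follows from the two rules as written. The first two worked cases hold at every ULN from 1.0 to 1.3 mg/dL and the third holds at any ULN. Only the fourth case and the width of the unit gap depend on the assumed ULN. The documents do not show how many patients are affected, and no harm is demonstrated.

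**What to change.** Reword the renal part of inclusion 8 to require serum creatinine <= 1.5 mg/dL **and** estimated creatinine clearance >= 50 mL/min (Cockcroft-Gault or 24-hour urine collection). This is the exact complement of the precaution and empties the overlap; keeping the present '> 50' would also do so. If the clinical team judges the looser rule safe, amend 4.1.10 to match inclusion 8 instead and say so.

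The text change is one line, but Section 9.4 requires a signed amendment with PRC and IRB approval. No new test is needed: the study calendars already collect creatinine and weight at screening. Tightening entry would make later patients differ slightly from those already enrolled, and it could turn away a man with clearance above 50 mL/min because of his creatinine alone.

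A few more screen failures are possible. With 14 of 43 enrolled by June 1, 2020, 29 places remained. If 2% to 10% of otherwise eligible men fall in the gap (an assumption), the extra men needed are 29 / 0.98 - 29 = 0.6 to 29 / 0.90 - 29 = 3.2. At the slower planned accrual of 2 per month, that is at most 3.2 / 2 = 1.6 months.
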